6.8.4 Vital Signs

Vital signs (temperature [C], pulse [bpm], blood pressure [systolic and diastolic, mmHg], oxygen saturation, and respiration rate [per min]), will be measured at Screening, Visit Weeks 4, 16, 28, 40 and 52 for all patients. In addition, vital signs will be collected at the following time points (± 10 minutes) in association with IT administration of idursulfase-IT, defined as IT vital signs: within 15 minutes prior to IT administration, 30 minutes post end of IT administration, 60 minutes post end of IT administration, 120 minutes post end of IT administration, and 4 hours post end of IT administration.

Vital signs will be plotted for individual patients over the time by scheduled study visit. The IT vital signs will be plotted for individual patients over the time by scheduled study visit from the start of the IT injection for each IT injection.

6.8.5 Physical and Neurological Examinations

Clinically significant physical and neurological examination findings will be recorded and summarized either as part of the medical history or adverse event data. No additional summary or listing will be provided.

6.8.6 Other Observations Related to Safety

6.8.6.1 Immunogenicity

Anti-idursulfase antibody formation will be monitored throughout the study for both serum and CSF. The number and percentage of patients testing anti-idursulfase antibody positive and negative at each scheduled time point will be summarized by treatment group. Antibody titer values will be plotted for individual patients over time by scheduled study visit in patients with positive antibodies at or prior to each scheduled visit. The neutralizing antibodies (NAb) titer will be plotted similarly for patients who developed positive neutralizing antibodies at or prior to each scheduled visit.

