2.3 Safety Objectives

- To determine the effect of the treatment regimen on safety as assessed by adverse events, clinical laboratory testing, physical and neurological examination findings, vital signs, and electrocardiogram (ECG) results
- To evaluate the anti-idursulfase antibody response in serum and CSF during the treatment regimen

2.4 SOPH-A-PORT Mini S Device Objectives:

- To determine the safety and performance of the SOPH-A-PORT Mini S device

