5.2 Inclusion Criteria

5.2.1 Inclusion Criteria for the Pivotal Study

Patients must meet all of the following criteria to be considered eligible for randomization in the pivotal study:

1. The patient is male and is ≥ 3 and < 18 years of age at the time of informed consent.

Note that patients who are younger than 3 years of age may be enrolled in a separate substudy provided that they meet other inclusion criteria, provided below.

2. The patient must have a documented diagnosis of MPS II. Of the three criteria below, the combinations (2a AND 2b) or (2a AND 2c) will be accepted as diagnostic of MPS II:
 - a. The patient has a deficiency in iduronate-2-sulfatase enzyme activity of $\leq 10\%$ of the lower limit of the normal range as measured in plasma, fibroblasts, or leukocytes (based on the reference laboratory's normal range).

AND

- b. The patient has a documented mutation in the iduronate-2-sulfatase gene that leaves the FMR1 and FMR2 genes intact.

OR

- c. The patient has a normal enzyme activity level of one other sulfatase as measured in plasma, fibroblasts, or leukocytes (based on the normal range of measuring laboratory).
3. The patient has evidence at Screening of Hunter syndrome-related cognitive impairment, defined as follows:

Note that separate inclusion criteria with respect to patient cognitive status at Screening apply to patients ≥ 3 and < 13 years of age and to patients ≥ 13 and < 18 years of age.

A patient who is ≥ 3 and < 13 years of age must have one of the following criteria (3a OR 3b):

- a. A GCA score ≥ 55 and ≤ 85

OR

- b. If the patient has a GCA score at Screening > 85 , there must be evidence of a decrease in GCA score of ≥ 10 points over 12 months from a previously documented test result in observational study HGT-HIT-090.

A patient who is ≥ 13 and < 18 years of age must have both of the following criteria (3c AND 3d):

- c. A GCA score of ≥ 55 and ≤ 85 .

AND

- d. There must be evidence of a decrease in GCA score of ≥ 10 points over 12 months from a previously documented test result in observational study HGT-HIT-090.
4. The patient has received and tolerated a minimum of 4 months of therapy with Elaprase during the period immediately prior to Screening.
5. The patient must have sufficient auditory capacity, with a hearing aid(s), if needed, in the Investigator's judgment to complete the required protocol testing and must be compliant with wearing the hearing aid(s), if needed, on scheduled testing days.

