6 STUDY TREATMENT

6.1 Description of Treatments

6.1.1 Investigational Product

The investigational product to be used in this study is idursulfase-IT for intrathecal use.

The idursulfase-IT drug product is an isotonic, sterile solution intended for IT administration. It is formulated as a 10 mg/mL protein concentration in 154 mM NaCl, pH 6.0, 0.005% polysorbate 20. It does not contain any preservatives and is intended for single use.

The active ingredient of the idursulfase-IT drug product is idursulfase (recombinant human iduronate-2-sulfatase) the same active ingredient in the commercially available drug Elaprase. However, Elaprase and idursulfase-IT are specifically formulated for the IV and IT compartments respectively; they cannot be interchanged.

In contrast to Elaprase, idursulfase-IT is specially formulated for, and compatible with, direct introduction into the IT space, because it is isotonic and contains excipients suitable for IT administration.

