6.6.1 Infusion Reactions and Management

Infusions of proteins can be associated with reactions to the infusion that may or may not be immune mediated (hypersensitivity reactions). Thus, potential reactions to the infusion of an investigational product, including idursulfase-IT, are unpredictable. It is often difficult to clinically distinguish infusion reactions from hypersensitivity reactions. Symptoms may include headache, fever, sensory paresthesias (including feeling of warmth, tingling, or pain), rash, pruritus, or autonomic symptoms, such as dry mouth or gustatory abnormalities (including loss of smell and metallic taste). Changes in mental status or level of consciousness that are not caused by pre-medication may either occur acutely or develop post-injection over time.

The management of infusion reactions and hypersensitivity reactions is similar. The following steps may be taken, at the discretion of the Investigator, in the event of a suspected infusion related/hypersensitivity reaction and the management of such reactions should be based on the severity of the reaction:

- Treatment with medications such as antihistamines, antipyretics, and/or corticosteroids
- Stopping and resuming treatment
- Pretreatment with antihistamines and/or corticosteroids may prevent subsequent reactions in those cases where symptomatic treatment was required

Infusion-related reactions have been observed in patients receiving IV enzyme replacement therapy (ERT) with Elaprase, with symptoms including cutaneous reactions (rash, pruritus, and urticaria), pyrexia, headache, hypertension, and flushing. Previous experience with Elaprase is fully described in the Elaprase US Package Insert and the EU Summary of Product Characteristics (SmPC). Pretreatment with antihistamines and/or corticosteroids may prevent subsequent reactions in those cases where symptomatic treatment was required. The safety information reported from administration of Elaprase may be relevant to management of adverse events in relation to idursulfase-IT.

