10.7.7.2 Immunogenicity

Anti-idursulfase antibody formation will be monitored throughout the study for both serum and CSF. The number and percentage of patients testing anti-idursulfase antibody positive and negative at each time point will be summarized by treatment group. Titer values will be summarized using box plots over time in patients with positive antibodies at or prior to each scheduled visit. The percent inhibition and titer will be plotted similarly for patients who developed positive neutralizing antibodies at or prior to each scheduled visit.

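### SAP 6.8.6.1 counts who is antibody positive at each visit, but does not define or count antibodies induced or boosted after IT treatment in boys already exposed to idursulfase

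*SAP*

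**What the plan says.** The safety objective (Protocol 2.3) is "To evaluate the anti-idursulfase antibody response in serum and CSF during the treatment regimen".

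All boys are exposed to the protein before the trial. Protocol 5.2.1 requires: "The patient has received and tolerated a minimum of 4 months of therapy with Elaprase during the period immediately prior to Screening". Protocol 6.1.1 describes the IT active ingredient as "the same active ingredient in the commercially available drug Elaprase". Both arms stay on Elaprase throughout (Protocol 6.2; SAP 4.1).

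SAP 6.8.6.1 plans three displays:

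- A per-visit table: "The number and percentage of patients testing anti-idursulfase antibody positive and negative at each scheduled time point will be summarized by treatment group".
- Titer plots: "Antibody titer values will be plotted for individual patients over time by scheduled study visit in patients with positive antibodies", limited to boys positive by the visit concerned.
- Neutralizing-antibody plots: "The neutralizing antibodies (NAb) titer will be plotted similarly for patients who developed positive neutralizing antibodies at or prior to each scheduled visit". The SAP does not say whether a boy who is neutralizing-antibody positive at Screening counts as having developed them.

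Protocol 10.7.7.2 has the same per-visit table, and also box plots of titer over time and plots of percent inhibition. SAP 6.8.6.1 uses individual plots and does not mention percent inhibition; SAP 7.2 does not list the difference. SAP 6.9.3 adds an assessment of the presence of antibodies against PK, if applicable. SAP 8.9 limits by-patient listings to those named in the text, and none is named for antibodies in the pivotal study.

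**The concern.** The objective concerns response, meaning change within a boy once IT dosing starts. The table reports prevalence, meaning how many boys are positive on a given day. In patients who had never met the protein the two would be close, because a positive result would be new. Here any boy may already be positive from Elaprase. The table counts him the same as a boy who converts after IT dosing, and it cannot register a rise in his titer.

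The SAP uses within-patient logic elsewhere. SAP 6.8.2 separates out boys whose laboratory values were normal or not clinically significant at baseline and became clinically significant later. Laboratory values, ECG, growth and intracranial pressure are also summarized as change from baseline. Immunogenicity, where prior exposure is universal, has no such step.

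What is at stake is whether one stated safety objective can be answered from a reproducible count. The primary and key secondary analyses are not involved.

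**Working it through.** The plan states no figure on this point, so there is none to reproduce. The check is whether the planned table can show the response, and whether the data for a better one already exist.

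**1. Antibody samples collected** (Protocol 7.11.10, 8.1.1, 8.3.2.1, 8.3.2.2, 8.3.3.2, 8.4.1, 8.4.2)

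| Sample | IT arm | No-IT arm |
|---|---|---|
| Serum | Screening, Weeks 4, 16, 28, 40, 52 | Screening, Weeks 4, 16, 28, 40, 52 |
| CSF | Screening, Weeks 4, 16, 28, 40, 52 | Screening, Week 52 |

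Week 4 is the first IT dosing visit. Its serum antibody sample is a pre-treatment assessment, and its CSF is drawn before the injection. Week 4 results therefore precede any IT drug, and the first serum result after IT exposure that both arms share is at Week 16.

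**2. What the per-visit table can show.** Let N be the boys in an arm, P the number positive before treatment, c the number who convert to positive and l the number who lose positivity.

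Percent positive later = 100 × (P + c − l) / N

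Induced rate among initially negative boys = 100 × c / (N − P)

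The table shows only the first quantity, which depends on c − l and not on c. Take N = 32 (the planned IT arm, SAP 4.1). The documents give no pre-treatment positivity, so assume 25%, 50% and 75%, with c = l = 4 as an illustration:

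| Assumed positivity | P | N − P | Later percent positive | Induced rate |
|---|---|---|---|---|
| 25% | 8 | 24 | (8 + 4 − 4)/32 = 25% | 4/24 = 16.7% |
| 50% | 16 | 16 | (16 + 4 − 4)/32 = 50% | 4/16 = 25% |
| 75% | 24 | 8 | (24 + 4 − 4)/32 = 75% | 4/8 = 50% |

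In each row the table shows no change.

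**3. Boosting.** Titer does not enter the formula for percent positive. If the titer of every initially positive boy rises, by any factor, the table moves by 0 points.

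**4. Neutralizing antibodies.** They are a named safety assessment (Protocol 3.4; SAP 4.1), but SAP 6.8.6.1 plans only a titer plot for them, with no number or percentage by arm.

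**The case against.** Four points on the other side have force.

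*The plan goes beyond percent positive.* A reader might infer that antibody results appear only as percentages, so that induced antibodies cannot be told from pre-existing ones. The documents do not support this. SAP 6.8.6.1 also plans individual titer and neutralizing-antibody plots, every boy has Screening serum and CSF results, and with about 48 boys the curves can show a conversion or a rise. The randomized no-IT arm, still on Elaprase, is a concurrent reference. What remains is that no rule says which rise counts, and no number results. The arm comparison is also thinner in CSF, where controls are sampled only at Screening and Week 52.

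*Chance imbalance at Screening is not the harm.* Randomization is not stratified by antibody status. The 95% chance range of the difference in positivity, 1.96 × √[p(1 − p)(1/32 + 1/16)], is ±24, ±28 and ±30 points at assumed p of 20%, 30% and 50%. A reader might infer that such an imbalance would pass for an IT effect. But Screening is a scheduled antibody visit, so its row would show the imbalance beside the later ones.

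*The added table will be sparse.* At 50% positivity, 16 and 8 boys start negative. If 20% of the IT boys convert (0.20 × 16 = 3.2), that is about 3/16 against 0/8, with a two-sided Fisher p of about 0.53. At 20% positivity the boosted row rests on about 6 and 3 boys (0.20 × 32 = 6.4; 0.20 × 16 = 3.2). This stands. All safety analyses are descriptive (SAP 6.8), so the table is for counting and not for testing.

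*Outputs not seen.* SAP Appendix I places table shells in separate documents, which may contain more. The SAP text requires nothing more.

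**Conclusion.** The point holds as a gap in definition and counting. SAP 6.8.6.1 does not define treatment-induced or treatment-boosted antibody against a boy's own pre-treatment status, does not count either by arm, and does not count neutralizing antibodies by arm. Followed as written, the table moves by 0 points for any titer rise in boys already positive, and can hide conversions offset by losses. The individual plots can show both, but only by eye.

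The offset example rests on assumed positivity of 25% to 75% and an assumed 4 conversions and 4 losses. The zero effect of boosting rests on no assumption. This is a worthwhile, low-cost improvement to a descriptive safety output. It does not show that the trial cannot detect an antibody response.

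**What to change.** Add to SAP 6.8.6.1 a by-arm table that places each boy in one class:

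- (a) negative before IT treatment and positive later;
- (b) positive before IT treatment, with a titer rise above a prespecified multiple of the assay dilution step;
- (c) positive before IT treatment and not boosted;
- (d) never positive.

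The denominator for (a) is boys negative before treatment, and for (b) boys positive before treatment.

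*Serum:* treat Screening and Week 4 as pre-treatment in both arms, state which of the two titers is the reference for a rise, and count events from Week 16 onward. Counting Week 4 as post-baseline would label a boy who converted on Elaprase alone as an IT case.

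*CSF:* compare the arms at Screening versus Week 52, and show the IT arm's Weeks 16, 28 and 40 results descriptively so that transient conversion is not lost.

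*Neutralizing antibodies:* give the same counts. Keep the per-visit table and the plots as supportive.

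The cost is SAP wording and a few tables from samples already scheduled. The titer-rise cut-off must be fixed in advance; the documents do not give the assay dilution step, so it must come from the assay validation. The counts will be small and should be presented as descriptive only.

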6.8.6.2 CSF Enzyme Level

Cerebrospinal fluid will be obtained from patients in the treated arm of the pivotal study and in the substudy at Screening, during surgical implantation of the IDDD, prior to each intrathecal injection of investigational product, and at the EOS visit.

The observed idursulfase enzyme levels in CSF will be plotted for individual patients before each IT dose over time by scheduled study visit. The descriptive statistics will be presented with the graph. If a measurement is <LLOQ, then it will be replaced by the zero value.

6.8.6.3 Height and Weight and Head circumference

Height (cm), weight (kg), and head circumference (cm) observed values and the change from baseline (Screening Visit) will be summarized by scheduled study visit and treatment group.

6.8.6.4 Intracranial Pressure (ICP)

ICP measurement (cm of H₂O) observed values and change from baseline will be summarized by scheduled study visit (Screening and EOS) and treatment group.

6.8.6.5 Brain MRI

The MRI measurements at baseline and the Visit Week 52, and the change from baseline to Visit Week 52 will be summarized descriptively by treatment group for the following parameters:

- Brain Total Intracranial Volume (cm³)
- Brain Total Tissue Volume (cm³)
- Brain Total White Matter (cm³)

- Brain Total Gray Matter (cm³)
- Total CSF Volume (cm³)

6.8.6.6 Hearing Assessments

The number and percentage of patients in the hearing assessment categories (right ear hearing aid, left ear hearing aid, and sufficient hearing for study assessments) will be summarized by treatment group, and visit (Screening, Visit Weeks 16, 28, 40 and 52).

6.8.6.7 Device Performance

Device-related terminology

- Initial device implant: The first IDDD implant that a patient ever receives.
- Partial device revision: Surgical revision/replacement of one or more component(s) of the device; other component(s) of the original device remain implanted and are not affected (e.g., port revision).
- Full device revision: The device is removed (explanted) in its entirety and a completely new device is implanted, including complete device removal with immediate replacement and delayed device implant after previous removal.
- Complete device removal with immediate replacement: Immediately implant of a new device after a device had been completely removed.
- Delayed device implant after previous removal: Implant of a new device after a previous device had been completely removed without immediate replacement on a separate and earlier occasion.
- Complete device removal without replacement: All parts of the device (both port and catheter) are removed and there is no new device implant.
- Device adjustment: surgical procedure of the device that is not a port replacement or full device revision.
- Device malfunction: The device does not perform as intended, based on the description in the device's Instructions for Use, but does not require either a partial or full device revision. If at the time of a scheduled dosing it is not possible to administer a full medication dosage as per the standard administration steps detailed in the device's Instructions for Use due to a device related issue, the IDDD will be declared a device malfunction. A device malfunction could be resolved without the need for a full or partial surgical revision. Programmatically it is when the malfunction date is present and outcome of malfunction is resolved.
- Device failure: When the device irreversibly fails to perform as intended and cannot be corrected without a device surgical intervention of either a partial or full device revision or removal. The IDDD will be declared a device failure, starting from the date of the initial malfunction that persists leading to the above surgical intervention. IDDDs that are considered to be malfunctioning at the end of the study will be categorized as Failures. For programming purposes, a device failure is when the malfunction date is present and outcome of malfunction is either ongoing or device failure (Surgical Procedure). The date of the device failure is the date of the initial malfunction.

- IDDD longevity: Total number of IDDD failures and explant divided by the total time at risk across all subjects in weeks (sum of time to IDDD failure or the last injection if not failed at the end of the data cut or explant date, from initial implantation, delayed implantation, or revision for all IDDDs).

Device Performance Analyses

SOPH-A-PORT[®] safety and performance will be summarized for IDDD-implanted patients in Safety Population. The number and proportion of patients of the following categories and the corresponding event count and event percentage will be summarized:

- Patients who had the initial implant only (i.e., no additional surgeries)
- Patients who had any post-initial implantation device surgeries
- Patients who had any type of difficulty associated with the implant procedure (e.g., difficulty accessing spinal canal, etc)

IDDD-related surgical procedure details for initial implants, complete removal with immediate replacement, and delayed implantation across all IDDD implantations for all patients will be summarized by failed or not failed IDDDs and overall, including incision region (paramedian vs. other), identification of the catheter passer used (Phoenix Neuro vs. other), number of suture wings implanted, suture wing configuration, interspace for catheter insertion into lumbar spine (L1-2, L2-3, L3-4, L4-5, L5-S1), spinal vertebral level of catheter tip (cervical, thoracic, lumbar and sacral), use of a purse string suture, use of the guidewire, orientation of the Tuohy needle and clinical site.

The number and proportion of patients who had at least one abnormal IDDD radiological assessment finding and the number of abnormal findings from the IDDD radiological assessments will be also summarized by types of the abnormality.

The number and proportion of patients and IDDDs with total malfunctions (including failure and malfunctions) as well as the corresponding event numbers will be presented. The types of IDDD malfunctions and the reasons for IDDD failures reported by the site and the Adjudication Committee will be summarized at the patient, IDDD and event level.

The annual event rate of IDDD failures and malfunctions will be calculated for each patient and the descriptive statistics will be summarized. The overall IDDD failure rate and its 95% CI will be presented. The overall IDDD failure rate is calculated as the total number of IDDD failures for all patients divided by the total IDDD time at risk, which is defined as the total time to IDDD failure or the last injection if IDDD is not failed at the end of the study, from initial implantation, or full device revision for all IDDDs. The overall IDDD malfunction rate is defined in the same manner.

The IDDD longevity (time to failure in weeks) and time to first total malfunction, for all implanted IDDDs, will be analyzed using the KM method. A new port identifies a new IDDD, starting from the date of implantation (either an initial implantation, a partial or full revision, or a

delayed device implant after previous removal). The time to IDDD failure (weeks) or total malfunction will be obtained by subtracting the date of the IDDD kit implantation from the date of IDDD failure (i.e., the initial malfunction date that persists leading to surgical intervention) or first total malfunction plus 1, and divided by 7, one decimal will be kept. IDDDs which did not fail or malfunction will be censored at the last study drug injection date for each IDDD. The number of IDDDs at risk, the cumulative number of IDDDs failed, censored, and the cumulative probability of failure with its standard error will be summarized in a table at each event time.

The proportion of patients for whom a successful first injection of investigational drug product occurred will be reported among those for whom a first injection was attempted (i.e., those who had an apparently successful implantation and did not suffer a device removal or revision prior to first scheduled injection). An injection is defined as study drug administered using IDDD. A successful injection is defined as the completion of study drug injection via IDDD without a malfunction. The proportion of patients who had no unsuccessful injection attempts during the study will also be summarized. Injections those are not successful for patient-related reasons (e.g., patient uncooperative, competing medical issue) will not be included in the determination of the injection success rate. The detailed list of the “Other” malfunction types will be reviewed by the Shire physician to determine if the injection was not given for patient reasons. If the injection is not given for patient reasons then it would not be counted as an unsuccessful injection attempt.

Whether any device component was implanted will be summarized for all IDDD kits which were opened. For the implanted IDDDs, their status (i.e. removed or not) at the end of the study will be reported. If an IDDD was removed, whether the catheter was removed along with the port will also be summarized.

An IDDD timeline of events (in weeks from implantation) including the timing of device surgeries (device adjustment, partial or full revision, and complete device removal without replacement), and malfunction and failure by IDDDs will be plotted by patient sorted by the duration since the initial implantation, longest on top.

The number of surgeries per patient will be presented by a bar chart. The types of IDDD malfunctions and failure per patient, as well as the reasons for the failures for the IDDDs reported by the site and the Adjudication Committee will be presented similarly by a bar chart.

The time from initial implant surgery to first IDDD failure and the time to first malfunction will be analyzed using the Kaplan Meier (KM) method for each patient who is in the Safety Population with IDDD implanted. The time to first IDDD failure or malfunction will be obtained by subtracting the date of the first IDDD implantation for the patient from the date of first failure or malfunction plus 1, divided by 7, and one decimal will be kept. Patients without an IDDD failure or malfunction will be censored at their last study drug injection date. The 25th percentile (Q1), median and 75th percentile (Q3) of the time to first failure or malfunction distribution and the 95% confidence interval (CI) will be presented together with the KM plots. A by-patient listing of the device failure and malfunction data will be displayed.

The IDDD longevity (time to failure in weeks) and time to first total malfunction, for all implanted IDDDs, will be plotted using the KM method. The 25th percentile (Q1), median and 75th percentile (Q3) of the time to failure or total malfunction distribution and the 95% CI will also be presented together with the KM plots.

The time (weeks) from IDDD implantation to failure/continuing function will be plotted as a horizontal bar chart for each device sorted by duration of each device implantation (time from the implantation of the corresponding IDDD), longest on top.

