4.3 Study Duration

The planned overall duration of each patient's participation in the study is approximately 14 to 15 months from Screening to the last scheduled contact.

An extension study is planned during which patients who complete HGT-HIT-094 and are eligible according to the inclusion/exclusion criteria for the extension study may continue, or begin, to receive IT treatment with idursulfase-IT via the SOPH-A-PORT Mini S device.

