7.5.4 Device Removal

If at the time of a scheduled dosing it is not possible to administer a full medication dosage as per the standard administration steps detailed in the device's IFU due to a device related issue, the IDDD will be declared a device malfunction. If the device malfunction is irreversible and cannot be corrected without a device surgical intervention, the IDDD will be declared a device failure, starting from the date of the initial malfunction.

The IDDD will then be surgically removed or revised and a new device and/or device components will be re-implanted at the earliest possible opportunity, preferably at the same time.

Details of the device removal will be recorded in the patient's CRF. For further details, please refer to the SOPH-A-PORT Mini S IFU.

Patients will have the IDDD removed when they discontinue from the study, unless the patient is continuing to receive treatment through another mechanism (eg, extension study, expanded access program).

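### SAP 6.8.6.7 defines device longevity in two conflicting ways, so planned removal of a working device is an event under one and censored under the other

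*SAP*

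**What the plan says.** Protocol 7.5.4 states: "Patients will have the IDDD removed when they discontinue from the study, unless the patient is continuing to receive treatment through another mechanism". Whether the device still works plays no part in that rule. The exception matters because Protocol 4.3 plans an extension in which "patients who complete HGT-HIT-094 and are eligible according to the inclusion/exclusion criteria for the extension study may continue, or begin, to receive" intrathecal treatment, so boys who enter it keep the device.

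SAP 6.8.6.7 then uses longevity in two places.

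- In the terminology list: "IDDD longevity: Total number of IDDD failures and explant divided by the total time at risk across all subjects in weeks". Time at risk runs from implantation to failure, last injection or explant. Explants are not limited by reason.
- In the analysis text, longevity is time to failure in weeks, estimated by Kaplan-Meier, with devices that did not fail censored at their last injection. Protocol 10.7.7.3 also treats longevity as time to failure.

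For programming, a failure needs a malfunction date and an outcome of ongoing or surgical procedure. Taking out a working device is therefore not a failure.

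On surgery, the SAP sorts implanted patients into "Patients who had the initial implant only (i.e., no additional surgeries" and "Patients who had any post-initial implantation device surgeries". The timeline plot covers "device surgeries (device adjustment, partial or full revision, and complete device removal without replacement". Removal is defined without a reason: "Complete device removal without replacement: All parts of the device (both port and catheter) are removed and there is no new device implant". A bar chart of surgeries per patient follows, also without a split by reason.

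**The concern.** Device longevity is a named assessment (Protocol 3.5 and 7.11.12, SAP 4.1) and serves the device safety and performance objective. If one event is counted under one definition and censored under another, two longevity figures from the same data will disagree, and the reader cannot tell which one the plan intended.

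The ratio also depends on something unrelated to the device: how many families stop rather than continue treatment elsewhere. A boy with a trouble-free port who leaves adds a longevity event. He also moves out of the initial-implant-only category into the group with later surgery, where he is listed alongside boys operated on because a device failed or caused a complication.

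**Working it through.** The documents state no re-operation, failure or longevity figure, so there is none to reproduce. The check applies the SAP's own definitions to one event: planned removal of a functioning device at study exit.

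**How each output in SAP 6.8.6.7 treats that event**

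| Output | Treatment |
|---|---|
| Longevity ratio (terminology list) | Counted as an event |
| Longevity by Kaplan-Meier, per device | Censored at last injection |
| Time to first failure or malfunction, per patient | Censored at last injection |
| Annual and overall failure and malfunction rates | Not counted |
| Any later device surgery | Counted, reason not shown |
| Surgeries-per-patient chart | Counted, if it uses the timeline plot's surgery list |

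**Formulas.** Let f be the number of device failures, k the number of boys whose only later surgery is removal of a working device, and T the device-weeks at risk.

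- Ratio as defined: (f + k)/T. Failures only: f/T. Inflation factor: (f + k)/f.
- Proportion with any later surgery: (f + k)/N as written; f/N for device-related surgery alone.

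**Inputs.**

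- N = 32, the planned treated group (SAP 4.1), taken as all implanted.
- Implant at Week 2 and last injection at Week 48, so 48 − 2 = 46 device-weeks per boy.
- Each failed device is replaced at once and counted once, with one failure surgery per affected boy.
- f = 4 and k = 3 are assumptions. The only nearby planning figure is up to 10% missing at Week 52 (SAP 4.2), which is not a rate of declining further treatment.

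**Longevity ratio, f = 4 and k = 3.**

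- Exit removals at Week 52: T = 29 × 46 + 3 × 50 = 1,484. As defined, 7/1,484 = 0.47 per 100 device-weeks; failures only, 4/1,484 = 0.27.
- Exit removals at Week 26: T = 29 × 46 + 3 × 24 = 1,406. As defined, 7/1,406 = 0.50; failures only, 4/1,406 = 0.28.
- In both cases the factor is 7/4 = 1.75.

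**Any later surgery.** 7/32 = 21.9% as written; 4/32 = 12.5% for device-related surgery alone. Each exit removal adds 1/32 = 3.1 percentage points.

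**Range, f = 2 to 16 and k = 1 to 6.** The factor runs from 17/16 = 1.06 to 8/2 = 4.0. The surgery proportion rises by 1/32 = 3.1 to 6/32 = 18.8 points. With k = 0 nothing changes.

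**Overall failure rate.** The numerator stays at f for every k.

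**The case against.** A reader might infer that SOPH-A-PORT event rates in general are overstated. The documents do not support that. The failure and malfunction rates and the Kaplan-Meier analyses all require a recorded failure or malfunction, and these are among the device measures that Protocol 10.7.7.3 names. None of them counts removal of a working device.

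A reader might also infer that the surgery category is wrong. It is not: taking out a port and catheter is an operation after the initial implant, and as a count of operations the category is correct. Dropping exit removals from it would leave operated boys either under a label that says they had no additional surgery or in neither category. It would also hide surgical burden. What remains is a matter of interpretation, because the category sits under device performance with no split by reason.

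The ratio appears only in the terminology list, and no sentence in the analysis text says it will be tabulated. That limits the practical effect, but it does not settle which definition governs a named assessment.

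The SAP also reports whether each device was removed by study end and plots surgeries beside malfunctions for each patient. A removal with no preceding malfunction can be seen there. The reason still cannot.

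Finally, the size is assumed. Boys who continue elsewhere keep the device, so k may be small or zero.

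**Conclusion.** The point holds in a limited form. The two longevity definitions in SAP 6.8.6.7 conflict, and the removal rule in Protocol 7.5.4 produces the very event on which they disagree. The ratio is inflated by (f + k)/f: 1.75 in the illustration, 1.06 to 4.0 over the range tried, and 1 if no working device is removed at exit. Those figures rest on assumed f and k, 32 implanted boys, immediate replacement of failed devices and one count per failed device. They are not trial data. The contradiction in wording exists whatever k turns out to be.

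The later-surgery category is accurate as a total but mixes two kinds of operation, and the surgeries-per-patient chart does the same if it uses the timeline's surgery list. A wider claim, that device failure or malfunction rates are biased, is not supported. This is a minor point, worth correcting because the edit is small.

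**What to change.** In SAP 6.8.6.7:

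- Keep one definition of longevity. Count as events device failures and removals for a device problem or complication. Censor planned removal of a functioning device at study exit, at the last injection as the SAP already does for devices that have not failed. If a rate per device-week is also wanted, use the same events.
- State explicitly that a removal for a complication is an event even without a malfunction date, since the programming rule for failure would otherwise miss it. The separate analysis of time to first failure can stay as it is.
- Leave the total count of later surgeries and the initial-implant-only category unchanged. Beneath the total, add two rows: surgery for device failure or complication, and planned exit removal of a functioning device. Use the same split in the surgeries-per-patient chart.

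The cost is SAP wording and one derived flag. Protocol 7.5.4 says only that details of the removal go on the case report form, so the sponsor should confirm that the reason for removal is among them. No clinical rule changes.
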